This study will add affect-based physical activity goals to an existing mHealth intervention called MyDayPlan, which delivers morning and evening goal sessions. Every Sunday, participants receive a text message with a link to a brief REDCap questionnaire where they are asked about their tentative sleep and physical activity schedule for that upcoming week. On days participants have planned to do physical activity (according to the Sunday scheduling survey), they will engage in two goal sessions: one in the morning and one in the evening. Participants are alerted to complete a session with a text message that has a link to a REDCap form. Morning goal sessions provide an activity goal for the day (“goal module”); ask the participant to create a concrete plan for achieving this goal (“action plan module”); and prompt the participant to anticipate barriers and brainstorm solutions to accomplish the goal (“coping plan module”). Evening goal sessions have participants reflect on whether they were able to meet this goal (“self-monitoring module”). The focus of the goal module differs according to the participant’s assigned condition. For each condition, the Fitbit Versa smartwatch will feature a custom watch face with a clock (current local time), the date, current device battery levels, and a physical activity button. The physical activity button can be pressed whenever a subject wants to engage in physical activity, and provides real-time feedback on activity duration. If the subject’s moving average HR is too low following the physical activity button press, the Fitbit smartwatch will ask “Still exercising?” twice (options No; Yes) before auto-concluding the session. [Note: for the Comparison Study, the wording of this question will be “Still being physically active?”]. Participants will also have the option to view short explanatory videos throughout their participation that summarize aspects of what is expected of them in the study.

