Two enhancements (TYPE/CONTEXT and SAVOR) will augment the treatment effects. TYPE/CONTEXT provides tailored recommendations for activity types and contexts that satisfy personally important psychological needs (i.e., relatedness, social esteem, individual esteem, creativity, mindfulness/reflection, learning, challenge, entertainment/escapism, aesthetic appreciation, morality) as rated by each participant at baseline. Ratings from a crowdsourced panel of adults on Amazon Mechanical Turk will be used to determine the potential for specific activity types³⁹ and contexts to satisfy psychological needs; our tailoring algorithm will then recommend the corresponding activity type or context while accounting for reported constraints (e.g., ability, access). These details will be incorporated into a tailored recommendation provided to participants during the Sunday Scheduling survey. Specifically, the program will randomly select either type or context (i.e., location, audio, social) recommendations and will rotate every two weeks. For TYPE, participants’ top 3 activity types are displayed in the following message: “THIS WEEK, we recommend trying [top 3 activity types] because it will satisfy your unique needs and make the experience more enjoyable.” For CONTEXT, participants’ top 3 activity contexts are displayed in the following message: “THIS WEEK, we recommend trying a physical activity [top 3 activity contexts] because it will satisfy your unique needs and make the experience more enjoyable.” SAVOR implements a brief savoring exercise on the smartphone that takes place either after the planned physical activity session or during the evening goal session (after the self-monitoring module). Participants will respond to questions that are intended to enhance and prolong positive experiences during physical activity. To trigger attentional deployment, a common savoring strategy that involves intensifying experiences by focusing on them,^{40,41} participants will answer two open-ended prompts. These prompts are drawn from a prompt pool with

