EMA via Fitabase Engage: Real-time prompted EMA (“check-ins”) will be administered on the smartwatch using Fitabase Engage. If no interaction with the watch face is made, one reminder signal may be emitted before the prompt becomes inaccessible. EMA (“check-ins”) take approximately 30 seconds to complete. If a prompt occurs during an incompatible activity (e.g., driving), participants will be instructed to ignore it. To minimize participant burden, all questions are answered by tapping the smartwatch interface.^{46,47} **Three types of EMA (“check-ins”)**—random, event-contingent, and evening—will be sent to participants. Random and event-contingent are used for the Formative Study, while the Comparison Study will use event-contingent and evening. **Random EMA** (“check-ins”) will be randomly scheduled to be sent during normal waking hours, with a single prompt sent during each of four evenly spaced time windows: 0-4, 4-8, 8-12-, and 12-16-hours post-waking. Participants are asked to report their incidental affect via seven bipolar Likert Scale items. Five items (Energetic-Fatigued, Happy-Discouraged, Relaxed-Tense, Excited-Bored, Satisfied-Frustrated) are drawn from Russell’s Circumplex Model of Affect;⁴⁸ one (Good-Bad) represents core affective valence;⁴⁹ and one (Proud-Embarrassed) represents self-conscious emotion.⁵⁰ One of these seven items is repeated as a validity check (i.e., for a total of eight items). **Event-contingent EMA** (“check-ins”) are triggered when Fitbit sensors detect physical activity via moving average heart rate max. At least a 10-minute buffer (Formative Study) or 30-minute buffer (Comparison Study) separates the first and second event-contingent EMA during a single exercise bout, such that the moving average heart rate is “reset” following completion of the first prompt and the earliest possible second prompt is sent at least 10-minutes later (Formative Study) or 30-minutes later (Comparison Study) assuming the aforementioned threshold is met. A maximum of two event-contingent EMA will be sent within any given 60 min period. Participants are asked to safely pause their activity to answer questions about their **affective response (mediator)**^{49,51,52} with the same eight (i.e., 7 unique + 1 repeated) items as the random EMA above. Event-contingent EMA also include end a Rating of Perceived Exertion (RPE) item and end by asking whether the current physical activity is the participant’s planned session.⁵³ Finally, evening EMA (“check-ins”) are sent to participants at 8 pm local time every day and ask participants to report their feelings from that day using the same eight affective response items as the random and event-contingent EMA (only modified to ask about their overall affect from that day, rather than their current affect). A depiction of the daily intervention strategies and measures is shown in Figure 2.

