
Figure 2. Daily eMOTION Intervention and Prompting Schedule

Note. ^a Used in the Formative Study; ^b Used in the Comparison Study.

REDCap surveys during morning and evening goal sessions are scheduled to be sent at the same time every day: 5:00 AM with approximately 5 reminders sent once every hour (morning goal session), and 6:00 PM with approximately 5 reminders sent once every hour (evening goal session). Sessions are sent via text message and completed via REDCap. These sessions will deliver the intervention components, as discussed above. Morning goal sessions also assess **affectively-charged motivations (mediator)**⁵⁴ with one item from the Attraction-Antipathy subscale of the AFFEXX,⁵⁵ and **anticipated affect (mediator)** with another item.⁵⁶ The morning goal session also measures incidental affective states using the same 7 items as the random and event-contingent EMA, stress,⁵⁷ pain,⁵⁸ fatigue,⁵⁹ illness, and sleepiness⁶⁰ as key **situational factors (moderator)**. Finally, the participant is asked whether they want to set a physical activity plan for that day, and whether their plan from the day before is the same or different from the plan they want to set for that day. Evening goal sessions measure **physical activity type** and **context (covariates)** by asking participants to report characteristics about the physical activity they performed that day (e.g., running, dance, hiking, home, park, alone, with spouse, perceived exertion⁵⁸). They are also asked if they enjoyed the activity they did (if receiving affect-based goals) and whether they focused on their goal during physical activity. Three questions ask about the extent to which that day's physical activity satisfied various psychological needs.

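### The evening goal session opens at a fixed 6:00 PM with no stated check that the planned activity is done, so evening exercisers can complete its retrospective items, and SAVOR when it sits in that form, before the bout

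*Combined protocol and SAP*

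**What the plan says.** **Send time.** Under Instrumentation (Methods, section 5), the protocol states "REDCap surveys during morning and evening goal sessions are scheduled to be sent at the same time every day". The evening session goes out at "6:00 PM with approximately 5 reminders sent once every hour (evening goal session".

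**When activity happens.** Under Intervention, the Sunday survey covers the week ahead: "they are asked about their tentative sleep and physical activity schedule for that upcoming week". The only stated use of that schedule for the goal sessions is to choose the days: "On days participants have planned to do physical activity (according to the Sunday scheduling survey), they will engage in two goal sessions". Exercise may take place at any hour: "The physical activity button can be pressed whenever a subject wants to engage in physical activity".

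**What the evening session asks.** Under Intervention, "Evening goal sessions have participants reflect on whether they were able to meet this goal". Under Instrumentation, it also asks for the type, context and perceived exertion of the activity performed that day, whether it was enjoyed (affect-based goals only), whether the participant focused on the goal, and how far the activity met psychological needs.

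**SAVOR.** It takes place "either after the planned physical activity session or during the evening goal session (after the self-monitoring module". The example prompts ask about the session done today. The text does not say what decides between the two routes.

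**The concern.** The form is retrospective, but its release depends on the clock and not on the activity. Take someone who plans a 7 PM walk and opens the 6 PM text. The form then asks about an event that has not happened. Any answer on goal attainment, type, context, enjoyment or needs cannot describe that walk. If SAVOR is delivered in the same form, its prompts have no completed planned session to work on.

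Two things are at stake. The first is SAVOR fidelity. H3 asks whether SAVOR strengthens the link between affective responses and affectively charged motivations and raises physical activity, and a savoring exercise completed before the bout cannot act on that bout. The second is the accuracy of the self-monitoring record and of type and context, which the protocol labels as covariates. Early completion would depend on exercise time, so the errors would gather among people who are active in the evening.

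**Working it through.** The plan states no figure on this point, so there is none to reproduce. The check has three parts.

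**1. Timing rules side by side.**
- Release: fixed at 6:00 PM on session days. Last reminder: 6 PM + 5 × 1 h = 11 PM, approximately.
- Activity: any hour, so after 6 PM is allowed.
- Content: refers to activity already performed.
- Safeguard: the text states no lock, no instruction to wait, no reopening of the form, and no flag for a form submitted before the activity.

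Early completion is therefore possible. Because reminders continue to about 11 PM, it is not forced.

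**2. Share of planned days affected (assumed).** The documents give neither exercise times nor response times. Let *e* be the share of planned sessions that start after 6 PM, and *c* the share of those in which the form is answered first. The affected share is *m* = *e* × *c*. I assume 10% to 50% for each:
- low: 0.10 × 0.10 = 0.01
- middle: 0.30 × 0.30 = 0.09
- high: 0.50 × 0.50 = 0.25

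So *m* runs from about 1% to 25%.

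**3. What that could mean for H3 (worst-case illustration).** The Data Analysis section gives *f*² = 0.04 for affective response, and 200 participants (100 per condition) after attrition for H2 and H3. Reading *f*² as a two-group contrast, which is my conversion, *d* = 2 × √0.04 = 0.4. With two-sided α = 0.05 and 80% power, *n* = 2 × (1.960 + 0.842)² / 0.4² = 98.1, so 99 per group and 198 in total. This agrees with the plan's 200, so the conversion is a usable yardstick.

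Suppose that all SAVOR went through the evening form and had no effect on affected days. The effect becomes *d* × (1 − *m*), and power = Φ(*d*(1 − *m*) × √(*n*/2) − 1.960). The second power column uses the enrolled 360 less 30% attrition: 360 × 0.70 = 252, or 126 per SAVOR level.

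| *m* | diluted *d* | power, 100 per group | power, 126 per group |
|---|---|---|---|
| 0 | 0.400 | 0.81 | 0.89 |
| 0.01 | 0.396 | 0.80 | 0.88 |
| 0.09 | 0.364 | 0.73 | 0.82 |
| 0.25 | 0.300 | 0.56 | 0.66 |

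This is an upper bound on the harm for a given *m*, because SAVOR has a second route. It is also a simple mean comparison. The plan's power came from Monte Carlo simulation, and the associational part of H3 is tested as a cross-level interaction.

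**The case against.** The case against is substantial, and much of it stands.

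- **Early completion is not forced.** Reminders to about 11 PM let an evening exerciser answer afterwards. This stands. A reader might infer that evening exercisers' records are generally wrong; the text shows only that they can be.
- **SAVOR has another route.** It may follow the planned session. This stands. A reader might infer that evening exercisers do not receive SAVOR on the right bout, but that can happen only when it is delivered inside the evening form. What remains is that nothing says which route applies on which day.
- **The main measures lie elsewhere.** Physical activity comes from the Fitbit. Affective response and exertion during a detected bout come from event-contingent EMA, and motivation from the morning session. This stands, so the outcomes are not corrupted as measurements.
- **SAVOR is randomized.** Exercise timing should be balanced between groups in expectation, so imperfect delivery dilutes an intent-to-treat contrast. Nothing here shows a directional bias.
- **H4.** A reader might infer that the mediation analysis is misclassified. The plan does not define intervention engagement, so this follows only if evening-form data feed it.
- **The 8 pm check-in.** It is "sent to participants at 8 pm local time every day" and might look mistimed too. It asks about overall affect that day and is not required to follow a bout, so it is not part of this point.
- **The logic may exist elsewhere.** The daily prompting figure is not shown, and the form's branching and the orientation content are not in the document. This is a fair limit: the point concerns what the text states, not what the live form does.

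The objection does not remove the core. The stated release rule permits a retrospective form to be completed before the event, and no stated rule detects it.

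**Conclusion.** The point holds in a limited form. The fixed 6:00 PM release, with no completion check, allows self-monitoring and the type/context, enjoyment and needs items to be answered before an evening bout, along with SAVOR when it is given in that form. The consequence is possible dilution of SAVOR delivery for H3 and some misrecorded self-monitoring and covariates.

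The size is unknown. About 1% to 25% of planned days rests wholly on the two assumed 10% to 50% ranges, and the power figures add the worst-case assumption that SAVOR used only the evening form. They show that the issue could range from negligible to material and are not an estimate. This is a worthwhile, inexpensive improvement and not a flaw that threatens the trial's conclusions.

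**What to change.** **Form.** Make the first evening item 'Have you finished your planned physical activity for today?'. Let 'not yet' close the form and leave the hourly reminders active. State that on such days SAVOR is given after the planned session, a route the protocol already allows. This is preferable to a send time computed from the planned end of activity, because the Sunday schedule is only tentative and no planned end time is mentioned.

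**Analysis.** In a sensitivity analysis, flag evening forms time-stamped before the bout that the participant identified as the planned session in the event-contingent EMA. Treat their goal-met, type/context and SAVOR fields as not assessed, rather than as 'no'. Do not flag against the last Fitbit bout of the day: that would void valid forms when an unplanned bout follows the planned session. Keep the intent-to-treat analysis as planned, since the flag depends on evening activity, which is part of the outcome. Report the flagged share, which would replace the assumed 1% to 25%. The time-stamp comparison can also be applied to data already collected, but only on days when the planned session triggered an answered check-in.

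**Cost.** One branching item, one sentence on the SAVOR route and one time-stamp comparison. Some forms will be completed later in the evening and a few will be missed.

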Intervention Period. The 19 weeks of study participation for the Comparison Study and three weeks for the Formative Study officially “start” on the first day of the run-in period. While everyone receives physical activity prescriptions, treatment delivery varies by group assignment (affect- or intensity-based goal setting), which is randomized for the Comparison Study. Morning and evening goal sessions, Fitbit wearing, and EMA (“check-in”) procedures are described in the Intervention and Instrumentation sections below. During the morning goal sessions, they also will complete a mobile Implicit Associations Tests (IAT) (i.e., called a “smartphone word match activity”) (for the sub-sample recruited to the Comparison Study n=120). Participants in the Comparison Study will additionally respond to a Mid-Study Questionnaire halfway through the study. Upon study completion, participants are asked to fill out a 30-minute REDCap questionnaire, with Formative Study and participants in the Comparison Study subsample recruited starting March 2025 (n=120) additionally completing an open-ended qualitative exit interview. The consent, orientation, and exit interview remote sessions are all scheduled by the participant using a Calendly integration. Periodic emails and text messages will also be sent to encourage study participants’ progress every few weeks.

The three-week Formative study (N=56) will iteratively test and refine the implementation of a novel treatment to manipulate affective mechanisms during physical activity. Acceptability and feasibility of content, delivery, device usage, engagement, and achieving clinically meaningful changes in affective mechanisms will be addressed.³⁶ Treatment components targeting intensity-based goals and affect-based goals will be tested separately in four groups of n=14 participants: [1] intensity-based goal setting alone; [2] affect-based goals + TYPE/CONTEXT; [3] affect-based goals + SAVOR; [4] affect-based goals + TYPE/CONTEXT + SAVOR. Testing occurs on a rolling basis with 1–2-week gaps to allow for iterative refinements.

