Mid-Study Questionnaire: Comparison Study participants will be asked to respond to a 30-minute REDCap questionnaire halfway through their participation in the study. This questionnaire will contain many of the same measures in the Baseline Questionnaire: demographics, general health, sleep schedule, depression, anxiety, life satisfaction, perceived stress, satisfaction of psychological needs through physical activity, physical activity enjoyment, exercise preference/tolerance, affective motivation and intrinsic motivation for physical activity, self-efficacy for physical activity, and physical activity intentions, attitudes, and identity. Participants also complete questions about their physical activity habits, as well as items about their sleep and mobility.

Post-Study Questionnaire: Participants will be asked to respond to a 30-minute REDCap questionnaire upon Formative Study completion. This questionnaire will contain the same questions as the Mid-Study Questionnaire, with additional items to assess the accessibility/usability and sustainability/feasibility of the interactive technology.⁹² A similar questionnaire will also be administered after the Comparison Study.

Exit Interview: Participants in the Formative Study, as well as a sub-sample recruited to the Comparison Study starting March 2025 (n=120), will engage in a 45-minute video conference exit interview to assess user experiences, accessibility/usability, burden, thoughts toward specific study components, and issues related to sustainability/feasibility.

Compensation

Participants will be compensated for their time and efforts based on measure completion. Participants in the Formative Study will receive up to \$75/three weeks: \$35 for wearing the Fitbit Versa smartwatch all day and night (≥ 23 h/day), \$35 for answering all Fitbit Versa smartwatch EMA (“check-ins”; with no more than one missed per day), and \$5 for completing the exit interview (Formative Study only).

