identified files in a limited-access encrypted Google Developer file system. Files are downloaded to secure USC servers for storage, processing, and analysis before being deleted from the Google system. Data will be downloaded from Fitabase servers and stored in a de-identified format on secure servers at USC that operate behind a firewall. Participants are assigned study-specific Fitbit accounts to use for the duration of the study; these accounts are deactivated (i.e., deleted through Fitbit.com by the study team) upon participant completion of the study. All Fitbit smartwatches returned to the study team (i.e., for the Formative Study or participants not finishing the Comparison Study) will be factory reset prior to being reused. Comparison Study participants who keep their Fitbit smartwatches will be instructed to create a new (private) Fitbit account for further use with the device. Participants will be informed of this during the informed consent process. All researchers with access to the data will undergo data sensitivity training specific to this project, beyond standard training required by our IRBs. Publications and presentations of study data will not contain any personal information about the participants. Breach of confidentiality is highly unlikely, given the de-identification and encryption of all sensitive information and materials. A master key linking participant names and ID numbers will be stored in a separate electronic location accessible only by the PI and Project Manager.

The majority of study staff will be blinded to participant assignment for most of the study period.

Data Analysis

Formative Study

For the Formative Study, DTx RWE Framework benchmarks will be assessed with descriptive statistics (e.g., mean scores, frequencies tallied and expressed as percentages of the sample). Most benchmarks explicitly specify the percentage (e.g., <1% or $\geq 51\%$ of participants) of the sample or the mean score of the scale/measure (e.g., System Usability Scale score ≥ 68 , Delighted-Terrible Scale score of 2-4) that define "success" for that benchmark. The analytic plan for the few benchmarks that are not explicit about the exact statistics used is outlined below. See also the attached document for more details.

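### Formative benchmarks that rest on exit self-report, notably the mean usability score, can reflect only participants who reached the end of the study

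*Combined protocol and SAP*

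**What the plan says.** Under Instrumentation, the Post-Study Questionnaire entry fixes the timing for the Formative Study: "Participants will be asked to respond to a 30-minute REDCap questionnaire upon Formative Study completion". The form repeats the Mid-Study content, "with additional items to assess the accessibility/usability and sustainability/feasibility of the interactive technology". The Intervention Period paragraph gives the same timing for both studies: "Upon study completion, participants are asked to fill out a 30-minute REDCap questionnaire". The same sentence adds the exit interview for Formative participants and for the Comparison sub-sample of 120. The interview is described as an "exit interview to assess user experiences, accessibility/usability, burden, thoughts toward specific study components, and issues related to sustainability/feasibility". Table 1 (Study Procedures) places both instruments in the Exit column. No questionnaire or interview at early withdrawal is described.

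Under Data Analysis, Formative Study, the benchmarks that define success are assessed descriptively: "mean scores, frequencies tallied and expressed as percentages of the sample". One example is "System Usability Scale score ≥ 68"; other examples are percentage thresholds of below 1% or at least 51%. The equity benchmark compares System Usability Scale scores by sex, race, ethnicity, age, BMI, income and physical ability, and is met if they are about equal. Further detail is deferred to an attachment that is not part of the supplied text. The only missing-data plan is under Comparison Study.

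**The concern.** The Formative Study exists to judge acceptability and feasibility and to refine the treatment. Someone who stops in week 2 because the watch, the prompts or the goals are unacceptable knows most about what needs changing. The plan as written describes no point at which that person is asked.

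A mean score can be computed only from people who gave one. If those who leave would have scored lower than those who stay, the usability mean rises because they left, and the threshold of 68 can be met for that reason. The equity benchmark has the same weakness: if one subgroup leaves more often because the programme does not suit it, the remaining members can look much like everyone else.

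The Comparison Study repeats the timing. There the cost is different: the usability answers and, in the sub-sample, the interviews would come from people who did not leave, while the sample-size paragraph expects about 30% attrition.

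**Working it through.** **Inputs.** Treatment components are "tested separately in four groups of n=14 participants", so 4 × 14 = 56, which reproduces the stated Formative sample size. The thresholds, a mean of 68 and 51% of participants, come from Data Analysis, Formative Study. No Formative dropout rate or score distribution is given, and there is no Formative power calculation to reproduce. The dropout numbers, the finisher mean of 70 and the stopper means below are assumptions.

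**Mean usability score.** Let N = 56, d the number who stop, F the finisher mean and S the mean that stoppers would have given. The all-starter mean is [(N − d)F + dS]/N. It is below 68 when S < [68N − (N − d)F]/d.

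- d = 6, F = 70: (68 × 56 − 50 × 70)/6 = (3808 − 3500)/6 = 51.3.
- d = 17, about 30%, a rate borrowed from the 19-week Comparison Study: (3808 − 39 × 70)/17 = (3808 − 2730)/17 = 63.4.

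As a dropout fraction, the finisher mean hides an all-starter mean below 68 once dropout exceeds (F − 68)/(F − S). With F = 70:

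- S = 40: 2/30 = 6.7%
- S = 50: 2/20 = 10%
- S = 60: 2/10 = 20%

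**Percentage benchmark of at least 51%.** With all 56 starters as denominator, 0.51 × 56 = 28.56, so 29 endorsements are needed whatever the dropout. With respondents as denominator, if no stopper answers:

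| Stoppers | Respondents | Endorsements needed | Share of 56 starters |
|---|---|---|---|
| 0 | 56 | 29 | 51.8% |
| 1 | 55 | 29 | 51.8% |
| 2 | 54 | 28 | 50.0% |
| 6 | 50 | 26 | 46.4% |
| 17 | 39 | 20 | 35.7% |

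One stopper cannot change the verdict, because 28/55 = 50.9% still fails. Two can: 28/54 = 51.9% passes on respondents, and 28/56 = 50.0% fails on starters if the two missing count as not endorsing. As bounds on starters, that case runs from 28/56 = 50.0% to 30/56 = 53.6%, so it would be undecided.

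**Which data are exposed.** Fitbit wear and activity, EMA check-ins and goal-session answers are collected during participation, including from people who later stop. The timing of the exit forms does not touch them.

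**The case against.** The strongest reply is that the documents nowhere say benchmarks are judged on finishers. That stands for the percentage benchmarks. A reader might infer a finisher denominator, but the text speaks of the sample and of participants without defining either. If starters are meant and non-response counts against the benchmark, dropout makes a 51% threshold harder to pass.

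Three other strong readings also go too far:

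- That exit timing favours every benchmark. Device usage and engagement are also Formative assessments, and they draw on data gathered during the study.
- That one leaver in a group of 14 reverses a verdict. No benchmark is said to be judged per group.
- That people who stop are barred from the forms. The plan is silent on them.

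It is also fair to say that the link between benchmarks and exit forms is partly inferred. The Post-Study Questionnaire entry does not name the System Usability Scale, though its usability items make it the natural place. The source of the 51% benchmarks is not stated, and the attachment may settle it. Dropout over three weeks, after a survey-willingness check, may be small. The success benchmarks are Formative only, and the Comparison Study plan mentions attrition propensity scores and sensitivity analyses.

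None of this answers the point about the mean. A score that was never collected cannot enter it, and the supplied Formative plan has no rule for its absence.

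**Conclusion.** The concern holds for Formative benchmarks built on exit self-report, chiefly the mean usability score and the subgroup comparison of those scores. Followed as written, they describe people who reached the end, and they can look favourable because dissatisfied people left. For percentage benchmarks the supported statement is narrower: the denominator is undefined in the supplied text.

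The size cannot be fixed from the documents. It depends on Formative dropout and on what stoppers would have said, neither of which is given. Under the assumed values, 6 stoppers of 56 matter if they would have averaged under 51.3 against a finisher mean of 70, and 2 stoppers matter for a 51% result at the boundary. These figures show that a benchmark could pass through selective dropout; they do not show that any has. The conclusion also assumes that the usability score comes from the Post-Study Questionnaire.

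**What to change.** 1. For participants still to be followed, send the existing usability items at the date of stopping as well as at completion, with the interview invitation where the interview applies.
2. For Formative data, report percentage benchmarks on all who started, and show non-response as best-case and worst-case bounds. Counting every non-answer as failure is only one convention, and bounds avoid having to choose it.
3. Report the usability mean with the number missing by group and the stopper mean that would bring it below 68, from the formula above.

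The protocol version is dated 04.02.25 and the Comparison Study was already recruiting, so Formative collection has probably ended. Items 2 and 3 can still be applied to the existing data; item 1 then serves the Comparison Study.

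The cost is a protocol wording change, one link sent at stopping, a few extra contacts and small payments. The current amounts are $15 for the Comparison post-study form, and $5 (Formative) or $20 (Comparison sub-sample) for the interview. The Formative payments, $35 + $35 + $5 = $75, include nothing for the questionnaire. Some benchmarks may become slightly less favourable.
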